4.2.2. Duration of Exposure to B/F/TAF Study Drug

Duration of exposure to B/F/TAF study drug will be defined as (the last B/F/TAF dose date B/F/TAF Study Day 1 + 1), regardless of temporary interruptions in study drug administration, and will be expressed in weeks using up to 1 decimal place (eg, 4.5 weeks).

Duration of exposure to B/F/TAF study drug will be summarized using descriptive statistics (n, mean, SD, median, Q1, Q3, minimum, and maximum) and as the number and percentage of subjects exposed for specified periods, ie, \geq 2 weeks (14 days), \geq 4 weeks (28 days), \geq 8 weeks (56 days), \geq 12 weeks (84 days), \geq 24 weeks (168 days), \geq 36 weeks (252 days), and \geq 48 weeks (336 days).

Summaries will be provided for subjects in the B/F/TAF Safety Analysis Set. No inferential statistics will be provided.

4.2.3. Adherence with Study Drug

Study drug adherence will be computed based on pill counts. The numbers of pills of study drug dispensed and returned are captured on the Study Drug Accountability eCRF.

Adherence (%) to E/C/F/TAF study drug will be calculated as follows:

$$\text{Adherence (\%)} = 100 \times \frac{\text{Total No. of pills taken}}{\text{Total No. of pills prescribed}}$$
$$100 \times \frac{\sum \text{No. of pills taken at each dispensing period}^{[1]}}{\sum \text{No. of pills prescribed at each dispensing period}^{[2]}}$$

- [1] Number of pills taken at a distinct dispensing period for a study drug is calculated as the minimum of (a) the daily number of pills prescribed for the study drug multiplied by the duration of treatment at the dispensing period, and (b) the number of pills taken for the study drug (number of pills dispensed minus the number of pills returned). Total number of pills taken is determined by summing the number of pills taken from all evaluable dispensing periods.
- [2] Number of pills prescribed at a distinct dispensing period for a study drug is calculated as the daily number of pills prescribed for the study drug multiplied by the duration of treatment at the dispensing period. Total number of pills prescribed is determined by summing the number of pills prescribed from all evaluable dispensing periods.

The duration of treatment at each dispensing period is calculated as the minimum of (a) the last returned date of study drug at a dispensing period, (b) date of premature discontinuation of the study drug, and (c) next pill dispensing date of the study drug, minus dispensing date of the study drug.

The next pill dispensing date is the following dispensing date of the study drug regardless of the bottle return date.

For a record where the number of pills returned was missing (with “Yes” answered for “Was Bottle returned?” question), it is assumed the number of pills returned was zero. If the number of pills dispensed was missing or any study drug bottle was not returned, or the bottle return status was unknown, then all records in that dispensing period will be excluded from both denominator and numerator calculation.

Adherence will be calculated using all data from the entire dosing period up to the date of permanent discontinuation of the E/C/F/TAF study drug for subjects who prematurely discontinued study drug or completed E/C/F/TAF study drug.

Descriptive statistics (n, mean, SD, median, Q1, Q3, minimum, and maximum) along with the number and percentage of subjects belonging to adherence categories (ie, < 80%, ≥ 80% to < 90%, ≥ 90% to < 95%, ≥ 95%) will be provided for subjects who return at least 1 bottle and have calculable adherence during the study in the E/C/F/TAF Safety Analysis Set. No inferential statistics will be provided.

Adherence will be calculated in a similar manner for the B/F/TAF Safety Analysis Set.

4.3. Protocol Deviations

A listing will be provided for subjects in the All Enrolled Subjects analysis set who violated at least 1 inclusion or exclusion criterion. The listing will include the criteria not met.

5. BASELINE CHARACTERISTICS

5.1. Demographics and Baseline Characteristics

Subject demographic data (eg, age, sex at birth, race, and ethnicity) and baseline characteristics (eg, body weight, height, and body mass index [BMI]) will be summarized using descriptive statistics (n, mean, SD, median, Q1, Q3, minimum, and maximum) for continuous data and by the number and percentage of subjects for categorical data. The summaries of demographic data and baseline characteristics will be provided for the E/C/F/TAF Safety Analysis Set and the B/F/TAF Safety Analysis Set. Baseline for each phase is defined in Section [3.8.1](#).

5.2. Baseline Disease Characteristics

The following baseline disease characteristics collected at enrollment will be summarized:

- Mode of infection (HIV risk factors)
- HIV disease status at study entry
- HCV antibody status at study entry
- Medical history at study entry: Type I or II diabetes (Yes/No), cardiovascular disease (Yes/No), hypertension (Yes/No), and hyperlipidemia (Yes/No) (see [Appendix 7](#) for details)
- Smoking status at study entry: (a) Never Smoked, (b) Former Smoker, and (c) Current Smoker (see [Appendix 7](#) for details)
- Duration of hemodialysis at study entry (years)
- Pre-switch ARV categories: (a) Containing TDF, (b) Containing ABC, and (c) Containing Neither
- Pre-switch ARV categories: (a) Containing 3TC, (b) Containing ABC, (c) Containing TDF, (d) Containing FTC
- Pre-switch ARV 3rd Agent Category: (a) INSTI, (b) PI, (c) NNRTI, (d) CCR5 Antagonist

The following baseline disease characteristics collected prior to E/C/F/TAF administration and prior to B/F/TAF administration will be summarized for the E/C/F/TAF Safety Analysis Set and the B/F/TAF Safety Analysis Set, respectively:

- HIV-1 RNA categories (copies/mL): (a) < 50 and (b) ≥ 50
- CD4 cell count (/µL)
- CD4 cell count categories (/µL): (a) < 50, (b) ≥ 50 to < 200, (c) ≥ 200 to < 350, (d) ≥ 350 to < 500, and (e) ≥ 500

- CD4%
- eGFR_{CG} (mL/min)

No inferential statistics will be provided.

5.3. Medical History

Subjects' answers to the following questions prespecified on the Medical History CRF will be listed:

- Does the Subject have diabetes? (Type I or II)
- Have any first-degree relatives experienced MI or stroke before the age of 50?

In addition, subjects' kidney transplant registration status collected by the Transplant History CRF will be listed.

General medical history data will be collected at screening and listed only. General medical history data will be coded using the current version of Medical Dictionary for Regulatory Activities (MedDRA).

6. ANALYSES OF PRIMARY ENDPOINT

6.1. Definition of the Primary Endpoint

The primary endpoint of this study is the incidence of treatment-emergent Grade 3 or higher AEs in subjects receiving E/C/F/TAF up to Week 48. The analysis of the primary endpoint was conducted for the Week 48 clinical study report and will not be repeated for this final analysis.

7. EFFICACY ANALYSES

The proportions of subjects with HIV-1 RNA < 50 copies/mL at Weeks 24 and 48 as defined by the US FDA-defined snapshot algorithm were summarized as part of the Week 48 clinical study report and will not be repeated for the final analysis.

7.1. Efficacy Endpoints as Secondary Study Endpoints

Secondary efficacy endpoints for the final analysis include the following:

- The proportion of subjects with HIV-1 RNA < 50 copies/mL at Week 96 as defined by the US FDA-defined snapshot algorithm
- The proportion of subjects with HIV-1 RNA < 50 copies/mL by visit
- The change from baseline in CD4 cell count and CD4% by visit

7.2. Analysis of Efficacy Endpoints

7.2.1. Analysis of the Proportion of Subjects with HIV-1 RNA < 50 copies/mL at Week 96 as Determined by US FDA-defined Snapshot Algorithm

US FDA-Defined Snapshot Algorithm

The analysis window at Week 96 is defined as from Study Day 631 to Study Day 714, inclusive. All HIV-1 RNA data collected on-treatment (ie, data collected up to 1 day after the last dose date of E/C/F/TAF study drug) will be used in the US FDA-defined snapshot algorithm. Virologic outcome for Week 96 will be defined using the following categories:

- **HIV-1 RNA < 50 copies/mL:** this includes subjects who have the last available on-treatment HIV-1 RNA < 50 copies/mL in the analysis window
- HIV-1 RNA \geq 50 copies/mL: this includes subjects
 - 1) Who have the last available on-treatment HIV-1 RNA \geq 50 copies/mL in the analysis window , or
 - 2) Who do not have on-treatment HIV-1 RNA data in the analysis window and
 - a) Who discontinue study drug prior to or in the analysis window due to lack of efficacy, or
 - b) Who discontinue study drug prior to or in the analysis window due to AE or death and have the last available on-treatment HIV-1 RNA \geq 50 copies/mL, or
 - c) Who discontinue study drug prior to or in the analysis window due to reasons other than AE, death, or lack of efficacy and have the last available on-treatment HIV-1 RNA \geq 50 copies/mL

- **No Virologic Data in Window:** this includes subjects who do not have on-treatment HIV-1 RNA data in the analysis window because of the following:
 - 3) Discontinuation of study drug prior to or in the analysis window due to AE or death and the last available on-treatment HIV-1 RNA < 50 copies/mL, or
 - 4) Discontinuation of study drug prior to or in the analysis window due to reasons other than AE, death, or lack of efficacy and the last available on-treatment HIV-1 RNA is < 50 copies/mL, or
 - 5) Missing data during the window but on study drug

The flowchart of the snapshot algorithm is provided in [Appendix 3](#).

The number and percentage of subjects with HIV-1 RNA < 50 copies/mL, HIV-1 RNA ≥ 50 copies/mL, and reasons for no virologic data at Week 96 will be summarized using the E/C/F/TAF FAS. The 95% confidence intervals (CIs) for percentages of subjects with HIV-1 RNA < 50 copies/mL and HIV-1 RNA ≥ 50 copies/mL will be constructed using the Exact method (see [Appendix Table 1](#)[Appendix Table 2](#)).

The same analysis will be repeated for proportion of subjects with HIV-1 RNA < 20 copies/mL at Week 96 as defined by US FDA-defined snapshot algorithm.

The Week 96 virologic outcomes for the US FDA-defined snapshot algorithm will be listed (see [Appendix Listing 2](#)).

7.2.2. Analysis of Other Efficacy Endpoints

7.2.2.1. By-Visit Analysis of the Proportion of Subjects with HIV-1 RNA < 50 copies/mL by Missing Failure and Missing Excluded Approaches

The proportion of subjects with HIV-1 RNA < 50 copies/mL will be summarized using the following 2 methods for imputing missing HIV-1 RNA values:

- Missing Failure (M F)

In this approach, all missing data will be treated as HIV-1 RNA ≥ 50 copies/mL. The denominator for percentages is the number of subjects in the E/C/F/TAF FAS.

- Missing Excluded (M E)

In this approach, all missing data will be excluded in the computation of the percentages (ie, missing data points will be excluded from both the numerator and denominator in the computation). The denominator for percentages at a visit is the number of subjects in the FAS with nonmissing HIV-1 RNA value at that visit.

For both M-F and M-E analyses, the number and percentage of subjects with HIV-1 RNA in the following categories will be summarized (see [Appendix Table 3](#)):

- < 50 copies/mL
 - < 20 copies/mL
 - < 20 Not Detectable
 - < 20 Detectable
- 20 to < 50 copies/mL
- \geq 50 copies/mL

The 95% CIs of the proportion of subjects with HIV-1 RNA < 50 copies/mL will be provided using the Exact method.

Separate summaries will be provided for the E/C/F/TAF FAS and the B/F/TAF FAS.

7.2.2.2. Analysis of CD4 Cell Count and CD4 %

Values and changes from baseline in CD4 cell count and CD4% will be summarized at each postbaseline visit using descriptive statistics based on observed on-treatment values. On-treatment values include data collected after the first dose date up to the applicable last dose date + 1 day for subjects who permanently discontinued the applicable study drug.

In addition, values and changes from baseline in CD4 cell counts with missing values imputed using the last observation carried forward (LOCF) method will be summarized at each postbaseline visit. The algorithm for LOCF is as follows:

- If a value is missing in an analysis visit window, the missing value will be replaced with the last on-treatment value (ie, up to 1 day after the last dose date of applicable study drug) observed before the analysis visit window that has the missing value.
- Baseline values will not be used for imputation; subjects who had no postbaseline CD4 assessment will be excluded from the postbaseline summaries.

The mean and 95% CI and median (Q1, Q3) of values and change from baseline in CD4 cell count over time will be plotted using observed data.

Separate summaries will be provided for the E/C/F/TAF FAS and the B/F/TAF FAS.

7.3. Changes From Protocol-Specified Efficacy Analyses

There are no changes from the protocol-specified efficacy analyses.

8. SAFETY ANALYSES

Safety data will be summarized for the subjects in the E/C/F/TAF Safety Analysis Set and the B/F/TAF Safety Analysis Set. All safety data will be included in data listings.

The primary endpoint of the incidence of treatment-emergent Grade 3 or higher AEs up to Week 48 was conducted for the Week 48 clinical study report and will not be repeated for this final analysis.

The secondary endpoint of the incidence of treatment-emergent Grade 3 or higher AEs up to Week 96 is defined in a similar manner to the primary endpoint included in the Week 48 clinical study report (See Section 8.1).

E/C/F/TAF Phase

For subjects who do not participate in the B/F/TAF OL extension phase, all safety data collected from the first dose of E/C/F/TAF up to 30 days after permanent discontinuation of E/C/F/TAF study drug will be summarized, unless specified otherwise. For subjects who participate in the B/F/TAF OL extension phase, all safety data collected up to the date of the first B/F/TAF study drug dose will be summarized, unless specified otherwise.

B/F/TAF OL Extension Phase

All safety data collected from the first dose of B/F/TAF up to 30 days after permanent discontinuation of B/F/TAF study drug will be summarized, unless specified otherwise.

8.1. Adverse Events Up to Week 96

Adverse events up to Week 96, or adverse events on or prior to Week 96, refers to those adverse events with onset date (if applicable) on or prior to the date of the Week 96 visit, as recorded on the Visit Date CRF, for subjects who had the Week 96 visit performed according to the Visit Date CRF.

If the onset date of an AE is partially missing (with only year and month or year alone), the event is considered on or prior to Week 96 if the month and year (or year alone) of the AE onset date is the same as or before the month and year (or year) of the Week 96 visit date recorded on the Visit Date CRF.

If the onset date of an AE is completely missing, the event is considered on or prior to the Week 96 if any of the following three criteria are met:

- The AE stop date is on or prior to the Week 96 visit date; or
- The AE stop date is partially missing, with the month and year (or year alone) on or prior to the Week 96 visit date; or
- The AE stop date is completely missing, including the case when AE is still ongoing.

For subjects who prematurely discontinued the study prior to the Week 96 visit, all adverse events will be considered AEs on or prior to Week 96.

8.2. Analysis of Adverse Events Up to Week 96

The number and percentage of subjects who experienced at least 1 Grade 3 or 4 treatment-emergent AE will be provided by system organ class (SOC) and preferred term (PT) using the E/C/F/TAF Safety Analysis set. For those AEs that occurred more than once in an individual subject during the specified time frame, the most severe grade will be used.

Multiple events will be counted only once per subject in the summaries. Adverse events will be summarized and listed first in alphabetical order of SOC, and then by PT in descending order of total frequency within each SOC. Grade 3 or 4 treatment-emergent AEs will also be summarized by PT only, in descending order of total frequency.

Grade 3 or 4 treatment-emergent study-drug related AEs by Week 96 will be summarized by SOC and PT.

The general safety summaries described in Section [8.3](#) will present all TEAEs (or subset of TEAEs).

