8.3.2. Adverse Event Severity

Adverse events are graded by the investigator as Grade 1 (mild), Grade 2 (moderate), Grade 3 (severe), or Grade 4 (life threatening) according to toxicity criteria specified in the study protocol. The severity grade of events for which the investigator did not record severity will be left as “missing” for data listings.

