8.3.3. Relationship of Adverse Events to Study Drug

Related AEs are those for which the investigator selected “Related” on the AE eCRF to the question of “Related to Study Treatment”. Events for which the investigator did not record relationship to study drug will be considered related to study drug for summary purposes. However, by-subject data listings will show the relationship as missing.

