8.3.5.2. Incomplete Dates

If the onset date of the AE is incomplete and the AE stop date is not prior to the first dose date of E/C/F/TAF study drug, then the month and year (or year alone if month is not recorded) of onset determine whether an AE is treatment emergent.

The event is considered treatment emergent for the E/C/F/TAF phase if both of the following 2 criteria are met:

- The month and year (or year) of the AE onset is **the same as or after** the month and year (or year) of the first dose date of E/C/F/TAF study drug, and
- The month and year (or year) of the AE onset is **the same as or before** the month and year (or year) of the date corresponding to the minimum of (1) the last dose of E/C/F/TAF study drug plus 30 days AND (2) the first dose of B/F/TAF study drug minus 1 day

The event is considered treatment emergent for the B/F/TAF OL extension phase if both of the following 2 criteria are met:

- The month and year (or year) of the AE onset is **after** the month and year (or year) of the first dose date of B/F/TAF study drug, and
- The month and year (or year) of the AE onset is **the same as or before** the month and year (or year) of the date corresponding to 30 days after the date of last dose of B/F/TAF study drug

An AE with completely missing onset and stop dates, or with the onset date missing and a stop date on or after the first dose date of E/C/F/TAF study drug, will be considered to be treatment emergent for the E/C/F/TAF phase. In addition, an AE with the onset date missing and incomplete stop date with the same or later month and year (or year alone if month is not recorded) as the first dose date of E/C/F/TAF study drug will be considered treatment emergent.

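### SAP 8.1 counts an AE of unknown onset as up to Week 96 if it is still ongoing, but drops it if it has a known stop date after Week 96

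*SAP*

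**What the plan says.** SAP Section 8 names the endpoint: "The secondary endpoint of the incidence of treatment-emergent Grade 3 or higher AEs up to Week 96". SAP 8.2 gives the count behind it: "The number and percentage of subjects who experienced at least 1 Grade 3 or 4 treatment-emergent AE will be provided". The breakdown is by MedDRA class and term, and the population is the E/C/F/TAF Safety Analysis Set.

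SAP 8.1 sets the time limit. For subjects who had the Week 96 visit, an event with a completely missing onset date counts as up to Week 96 if any one of three criteria is met. The first is that it ended no later than the visit. The second is that its stop date is incomplete and the known part falls no later than the visit. The third is worded as follows: "The AE stop date is completely missing, including the case when AE is still ongoing".

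For subjects who left the study before the Week 96 visit, every event counts. A partial onset date counts if its month and year, or its year alone, is no later than that of the visit.

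SAP 8.3.5.2 settles treatment emergence for the whole E/C/F/TAF phase. An event "with the onset date missing and a stop date on or after the first dose date of E/C/F/TAF study drug, will be considered" treatment emergent for that phase.

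**The concern.** The three criteria leave a gap. An event with no onset date and a known stop date after the Week 96 visit satisfies none of them and is excluded. An event with no onset date that is still ongoing is included. Both were present after Week 96, and neither record shows whether the event began before or after the visit. The only difference is that one has since resolved.

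If anything, the recorded stop date favours counting. Onset cannot be later than the stop date, so an event that ended shortly after the visit very probably began before it. An ongoing event has no such upper bound, yet it is the one counted.

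The endpoint is a secondary safety endpoint in a single-arm trial of 55 subjects, so a single subject is visible in the percentage. SAP 2.4 says a Week 96 analysis has already been done. If it used the same rule (the documents do not show this), an event counted then as ongoing could leave the final figure only because it later resolved.

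**Working it through.** **The plan's own figure.** SAP 1.3 assumes a 10% rate and n = 50. The normal approximation gives 0.10 ± 1.96 × √(0.10 × 0.90 / 50) = 0.10 ± 0.083, or 1.7% to 18.3%, as stated. It does not depend on the date rules and only confirms the planning precision.

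**Applying the rule.** Assume, for illustration, a Week 96 visit on 15 March 2018, a first E/C/F/TAF dose on 1 May 2016 and a completely missing onset date.

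| Stop date on record | Counted up to Week 96 (SAP 8.1)? | E/C/F/TAF treatment emergent (SAP 8.3.5.2)? |
|---|---|---|
| 15 March 2018 | yes | yes |
| 16 March 2018 | **no** | yes |
| 1 December 2018 | **no** | yes |
| March 2018, day missing | yes | yes |
| December 2018, day missing | **no** | yes |
| 2018 only | yes | yes |
| 2019 only | **no** | yes |
| missing | yes | yes |
| ongoing | yes | yes |

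The second row is the clearest case. That event must have begun by 16 March 2018, so it falls after the visit only if it began on that single day. It is excluded, while the ongoing event in the last row is counted.

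**Can the case arise?** Yes. US subjects continue E/C/F/TAF with 12-weekly visits after Week 96 (SAP 1.2), and events are followed until resolved or stable where possible (Protocol 7.3.1). Stop dates after Week 96 can therefore be recorded.

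**Scale.** The E/C/F/TAF Safety Analysis Set is 55 in the SAP's mock disposition table (Appendix 6), matching the Week 48 results in Protocol 1.2.5. Each affected subject with no other qualifying event moves the estimate by 1/55 = 1.8 points. The documents give no Week 96 count. As an illustrative base, take the 20 of 55 subjects with Grade 3 or 4 events through the Week 48 report's data cut (Protocol 1.2.5). Exact (Clopper-Pearson) limits are the 0.025 quantile of Beta(x, n − x + 1) and the 0.975 quantile of Beta(x + 1, n − x):

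| Subjects added | Estimate | Exact 95% CI |
|---|---|---|
| 0 | 20/55 = 36.4% | 23.8% to 50.4% |
| 1 | 21/55 = 38.2% | 25.4% to 52.3% |
| 2 | 22/55 = 40.0% | 27.0% to 54.1% |

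The range of 0 to 2 subjects, or 0 to 2/55 = 3.6 points, is an assumption.

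**The case against.** Three objections carry weight.

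First, a reader might infer that SAP 8.1 contradicts SAP 8.3.5.2, since the same event is treatment emergent under one and absent under the other. It does not. SAP 8.3.5.2 covers the whole E/C/F/TAF phase, which runs past Week 96, and SAP 8.1 takes a time subset of it. A phase event can properly fall outside the subset. The inconsistency lies within SAP 8.1.

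Second, a reader might infer that the endpoint as a whole is biased downwards. That is not supported either. Most of the other missing-date rules in SAP 8.1 lean towards counting: same-month or same-year partial onset, a year-only stop date in the year of the visit, a missing stop date, and every event in early leavers. The net direction is not fixed. Some excluded events will also have begun after Week 96, and leaving those out is correct.

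Third, little is hidden. An excluded event graded 3 or 4 still appears in the whole-phase Grade 3 or 4 summary and in the listings (SAP 8.3.6). An affected subject also needs a completed Week 96 visit, no onset date at all, a known later stop date and no other qualifying event. A shift of 1.8 points is small against an interval about 27 points wide, and no formal testing is planned (SAP 3.5).

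None of this explains why an ongoing event counts and a later-resolved one does not. One can argue that a missing stop date says nothing about timing and so defaults to inclusion. That argument does not extend to an event recorded as ongoing, which is known to have lasted past Week 96.

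**Conclusion.** The point holds as a drafting inconsistency within SAP 8.1 and is a cheap improvement. For subjects who had the Week 96 visit, two events with equally unknown onset are treated differently because one has a recorded resolution date. Taken alone, the rule can lower the Week 96 Grade 3 or higher incidence by 1.8 points per affected subject with no other qualifying event. The number affected is unknown and may be zero. The percentages above rest on n = 55, an illustrative base of 20 subjects and an assumed range of 0 to 2 affected.

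A reader might also infer from SAP 8.3.2 that ungraded events drop out of the endpoint and should be counted as Grade 3. The text says "The severity grade of events for which the investigator did not record severity will be left as" missing, but only for listings. It gives no rule for summaries. Exclusion has to be inferred from the general no-imputation default in SAP 3.6.1. SAP 8.3.3 is not a close model, although it does say "Events for which the investigator did not record relationship to study drug will be considered related to study drug for summary purposes": relationship is a yes or no item with one conservative default, whereas severity has four grades and Protocol 1.2.5 reports that most events were Grade 1 or 2. The protocol's grading requirement (7.2.2) and data queries (9.1.6) should also leave few such records. Imputing Grade 3 is therefore not recommended.

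**What to change.** In SAP 8.1, replace the three stop-date criteria with one sentence: an E/C/F/TAF treatment-emergent AE with a completely missing onset date is counted as on or prior to Week 96 regardless of its stop date, unless other recorded data show onset after the Week 96 visit or on or after the first B/F/TAF dose. The second exception is needed because SAP 8.3.5.2 sets no upper limit on the stop date when onset is missing, so an event known to have begun on B/F/TAF could otherwise be attributed to E/C/F/TAF.

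Footnote the number of events counted this way, so that any difference from the Week 96 analysis already done can be traced. At most, add a footnote giving the number of treatment-emergent AEs with no recorded grade.

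The cost is one SAP sentence, a small program edit and the footnote. The downside is that an event that in fact began after Week 96 could be counted, making the figure slightly less favourable.
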